Eligibility Criteria (continued):	
Exclusion criteria:
 
1. History of chronic liver disease with elevated liver function tests, chronic kidney disease (stage 3 or greater, eGFR <60 mL/min), uncontrolled thyroid disease (elevated thyroid function tests), primary or secondary hyperparathyroidism, hypercalcemia, or multiple endocrine neoplasia.2. Hypercalcemia defined as either elevated corrected serum calcium >10.2 mg/dL) measured within 3 months prior to study.3. eGFR <60 mL/min within 3 months prior to study.4. Active cancers5. Women who are pregnant or breastfeeding.6. Individuals who are unable to give informed consent7. Individuals with psoriasis, active eczema or other skin disease, or who are currently receiving treatments or medications for skin disease.8. Individuals who do not agree to refrain from using tanning beds for the duration of the study.9. Individuals who do not agree to avoid submerging the gel site in water for 8 hours after gel application.10. Family members of the study faculty or staff.
--	--

Study Procedures: (Including pharmacokinetic (PK) sampling times)
	
The following procedures will be performed during this study:
 
 • Chart review to assess for potential eligibility • Day 0 
 ○ Subject informed consent ○ Measurement of height and weight and examination of skin for rash/appearance to confirm eligibility ○ Record Fitzpatrick skin test score. ○ Blood draw for baseline vitamin D levels (total vitamin D 25-OH and vitamin D3) ○ Blood draw for serum creatinine (for GFR calculation), albumin (for corrected calcium) and parathyroid hormone ○ Application of Vitamin D gel by study staff to inside of each arm ○ Instruct subject on assessment of skin. If any rash or other skin reaction appears, contact the clinic as soon as possible for an assessment. • Day 7 
 ○ Assessment of skin for rash or other reaction ○ Draw blood for Ca, vitamin D level. ○ Application of Vitamin D gel by study staff to inside of each arm. • Day 14 
 ○ Assessment of skin for rash or other reaction ○ Draw blood for Ca, vitamin D level. ○ Application of Vitamin D gel by study staff to inside of each arm. • Day 21 
 ○ Assessment of skin for rash or other reaction ○ Blood draw for post dose vitamin D, calcium, and parathyroid hormone level.

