
Safety
	
All subjects will be monitored for skin rash or other reactions. Any rash and/or reaction will be photographed by study staff and assessed/diagnosed by a physician.
 
Patient will have serum calcium followed each week during the study. Although it is unlikely that calcium will change with an increase in topical Vitamin D, hypercalcemia presents a potential theoretic risk if absorption is high or unexpected variability in vitamin D absorption exists.

Laboratory Parameters/Analysis:
	
Laboratory analyses will consist of 25-hydroxyvitamin D blood levels (D2 and D3) and parathyroid hormone levels. For safety, an albumen adjusted calcium determination will be measured on day 0, 7, 14, and 21.

Total Blood Volume:
	
Approximately 5 mL will be required at day 0, 7, 14, and 21 to assess for vitamin D parameters and safety.

Sample Size Determination: (If applicable)	The study will have 20 subjects who are evaluable for changes in vitamin D blood levels.
Statistical Analyses: (Brief Description)	Two sample paired t test of pre and post total vitamin D and parathyroid hormone with an alpha of .05. We do not expect any significant change in adjusted calcium.

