8.2 Exclusion Criteria

Subjects are excluded from this study if any of the following conditions are met:

1. History of acute or chronic liver disease with elevated liver function tests, chronic kidney disease (stage 3 or greater, eGFR <60), uncontrolled thyroid disease (elevated thyroid function tests), primary or secondary hyperparathyroidism, hypercalcemia, or multiple endocrine neoplasia.
2. Hypercalcemia defined as elevated corrected serum calcium (>10.2 mg/dl) measured within 3 months prior to study.
3. eGFR <60 mL/min within 3 months prior to study.
4. Active cancers
5. Women who are pregnant or breastfeeding
6. Individuals who are unable to give informed consent
7. Individuals with psoriasis, active eczema or other active skin disease, or who are currently receiving treatments or medications to control skin disease
8. Individuals who do not agree to refrain from using tanning beds for the duration of the study.
9. Individuals who do not agree to avoid submerging the gel site in water for 8 hours after gel application.
10. Family members of the study faculty or staff.

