11.1 Baseline Assessments

A chart review of subjects with known vitamin D deficiency will be performed prior to Day 0 in order to assess for potential study eligibility. Informed consent must be obtained before any study procedures are performed.

11.1.1 Study Day 0

The following procedures should be completed on Day 0:

- informed consent
- assessment of height, weight and skin to assess for study eligibility
 - Anthropometric Assessment
 - Patients are measured for height (cm) and weight (kg) following standardized procedures as outlined in the Anthropometric Standardization Reference Manual (Lohman et al., 1991). Body weight is measured with a stand-on digital scale and height is measured by a stadiometer. Height is measured to the nearest 0.1 cm and weight to the nearest 0.1 kg.
 - Recording of Fitzpatrick skin-type score.
- Blood draw for vitamin D level, parathyroid hormone level, calcium, and albumin.
- Application of the topical vitamin D gel, including instructions for dosing at home

11.1.2 Study Day 7 and Study Day 14

- Evaluation of skin site where gel applied. If the subject has any skin rash or other reaction, he/she should contact study personnel as soon as possible for photographs and an assessment/diagnosis
 - Photographs of application sites
 - A digital photograph may be taken of the gel application site following application to record any signs of irritation or reaction. Identifying marks on or near the application site (i.e. tattoos, birthmarks, scars etc.) should be avoided when a photograph is taken. Digital photographs will be uploaded to the REDcap database and stored on the secure server.
- Blood draw for vitamin D level and calcium
- Application of the topical vitamin D gel

11.1.3 Study Day 21

- Assessment of skin for rash or any other reaction
- Blood draw for vitamin D, parathyroid hormone level, and calcium.

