We will initially administer 100,000 units topically to subjects, and check serum Vitamin D and calcium levels one week later. Dosing will be discontinued if a patient achieves a Vitamin D level of greater than normal (> 90 ng/ml) or if serum calcium rises above normal (> 10.2 mg/dl). Additional doses of 100,000 units will be administered on days 7 and 14. The outcome of interest will be the effect on total serum Vitamin D at 21 days. Although a change in calcium is unlikely, calcium will be monitored for safety.

Vitamin D may alter glucose values and improve glucose control in individuals with diabetes²⁶. Although individuals with diabetes will not be excluded, we will instruct any subjects with diabetes to more closely monitor glucose values during the course of the study.

Parathyroid hormone will be measured at baseline and on Day 21 to determine if vitamin D correction changes the level of this metabolic calcium regulatory hormone.

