14.1 Analysis Populations

Safety Population: all subjects who receive at least 1 dose of study drug and who have at least one post-dosing safety evaluation. All safety endpoints, baseline characteristics, and demographic data will be summarized using the Safety Population.

Efficacy Evaluable Population: all subjects who receive all 3 doses of study drug and have a follow up blood draw for vitamin D levels, or discontinue prior to completing dosing due to a drug-related adverse event. Vitamin D level data will be analyzed using the Efficacy Evaluable Population.

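### The calcium dosing stop uses uncorrected serum calcium, while entry and safety monitoring use albumin-corrected calcium, and no albumin is scheduled on Days 7 and 14

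*Protocol*

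**What the plan says.** **Stopping rule.** Protocol section 13.1.1 ends dosing on either of two laboratory results: vitamin D above 90 ng/ml, "or if serum calcium rises above normal (> 10.2 mg/dl"). It does not say the calcium is corrected. This is the only calcium-based dosing stop in the Protocol or the SAP. Sections 8.3 and 15.8 give only general reasons for withdrawal and termination.

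**Entry.** Section 8.2 excludes "Hypercalcemia defined as elevated corrected serum calcium (>10.2 mg/dl) measured within 3 months prior to study". The Synopsis has the same criterion: "Hypercalcemia defined as either elevated corrected serum calcium >10.2 mg/dL) measured within 3 months prior to study".

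**On-study safety measure.** The Synopsis, under Laboratory Parameters/Analysis, states: "For safety, an albumen adjusted calcium determination will be measured on day 0, 7, 14, and 21". Its statistical row also refers to adjusted calcium.

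**What is drawn.** On Day 0 the Synopsis lists "albumin (for corrected calcium) and parathyroid hormone", and section 11.1.1 includes albumin. For Days 7 and 14 the Synopsis has "Draw blood for Ca, vitamin D level" and section 11.1.2 has "Blood draw for vitamin D level and calcium". Table 1 schedules calcium on all four days and albumin on Day 0 only. The Day 21 lists in the Synopsis and section 11.1.3 also omit albumin.

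**The concern.** The protocol defines hypercalcaemia by corrected calcium above 10.2 mg/dl at entry and plans to monitor the corrected value. It then stops dosing on an uncorrected value at the same limit and gives no reason for the change. Staff who follow section 13.1.1 with the visit lists would compare the uncorrected result with 10.2 and would have no same-day albumin to correct it.

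The error can go either way. At low albumin, a subject whom the entry definition would call hypercalcaemic goes on to another 300,000 IU. At high albumin, a subject who is normal by that definition loses the remaining doses. Two people could reach opposite dosing decisions on the same sample, each citing the protocol. The Synopsis itself names hypercalcaemia as a possible risk if absorption is high or unexpectedly variable.

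There is a secondary effect on the analysis. The Efficacy Evaluable Population (Protocol 14.1, SAP 1.1) needs all three doses, but it also keeps subjects who "or discontinue prior to completing dosing due to a drug-related adverse event". A needless stop before dose 3 therefore removes a subject only if it is not classed as a drug-related adverse event.

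**Working it through.** **1. The texts side by side**

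| Place | Calcium quantity | Albumin available that day? |
|---|---|---|
| Entry (8.2, Synopsis) | corrected, limit 10.2 mg/dl | implied by the criterion |
| Safety measure (Synopsis) | adjusted, Days 0, 7, 14, 21 | Day 0 only |
| Dosing stop (13.1.1) | serum, limit 10.2 mg/dl | not on Day 7 or 14 |

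If the stop means uncorrected calcium, it contradicts the entry definition and the planned safety measure. If it means corrected calcium, the schedule does not supply the input. Either reading needs an edit, and this holds without any arithmetic.

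**2. Size of the gap in one subject**

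The documents give no correction formula. Assume corrected = measured + c × (4.0 − albumin in g/dl), with c = 0.8.

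- Albumin 3.5: 10.2 + 0.8 × 0.5 = 10.6, so corrected values from just above 10.2 up to 10.6 are missed.
- Albumin 4.0: 10.2, so the two definitions agree.
- Albumin 4.5: 10.2 − 0.8 × 0.5 = 9.8, so corrected values from just above 9.8 up to 10.2 cause a needless stop.

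For c from 0.6 to 1.0, the measured calcium equivalent to corrected 10.2 is 9.7-9.9 at albumin 3.5 and 10.5-10.7 at albumin 4.5.

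**3. Expected frequency (simulation, all distributions assumed)**

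There were 24 scenarios of 1,000,000 subjects each:

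- albumin mean 4.0, 4.2 or 4.4 and SD 0.30 or 0.35, constant within a subject;
- calcium mean 9.4 or 9.6, total SD 0.35 including within-subject SD 0.2;
- albumin-calcium correlation 0.3 or 0.6;
- no gel effect;
- corrected calcium at most 10.2 at entry and serum calcium at most 10.2 on Day 0.

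| Event | Range | Of 20 subjects |
|---|---|---|
| Needless stop, Day 7 | 0.5-2.9% | 0.1-0.6 |
| Needless stop, Day 7 or 14 | 0.9-5.0% | 0.2-1.0 |
| Missed, Day 7 | 0-2.2% | 0-0.4 |
| Missed, Day 7 or 14 | 0-3.8% | 0-0.8 |

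The two upper limits do not occur together. Where needless stops are most frequent, missed cases are at most 0.05%.

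Sensitivity of needless stops on Day 7 or 14: without the Day 0 condition they are 1.2-7.1%. If total SD is also raised to about 0.40 (√(0.35² + 0.2²)), they are 1.9-9.9% (0.4-2.0 of 20). With the Day 0 condition and calcium mean 9.2, they can fall to 0.2%.

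**4. Effect on precision**

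The inputs are those of Protocol 14.4 and SAP 1.4: SDs 4 and 12, difference 10 µg/L, two-sided alpha 0.05. Treating the two measures as uncorrelated, the SD of the difference is √(4² + 12²) = 12.65. Paired t-test power is 91.8% with 20 subjects, 90.3% with 19 and 88.5% with 18.

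**The case against.** The strongest reply is that the practical risk is small and largely covered.

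- **The vitamin D stop.** The same sentence also stops dosing above 90 ng/ml, which needs no albumin, and section 5.1 puts concern about hypercalcaemia above 150 ng/ml. This stands as a reason for a moderate rating. It does not make the calcium criterion right, since the protocol chose to have one.
- **Shorthand.** The wording in 13.1.1 may be short for the adjusted value that the Synopsis defines. That is possible, but then albumin is missing from the Day 7 and 14 lists.
- **Carrying Day 0 albumin forward.** In healthy adults, with liver disease with elevated liver tests, eGFR below 60 and active cancer excluded, this would be reasonable over 14 days. The simulation holds albumin constant within a subject, so it measures the effect of the wording and gives no evidence that repeat assays matter. That point stands. No text provides for carry-forward, however, and the Synopsis commits to an adjusted determination on each day.
- **Day 14.** Gel is applied at the visit where blood is drawn, and no same-day result is promised. A Day 14 result that arrives after dose 3 changes no dosing, so the Day 7 figures are the ones to weigh.
- **Direction.** At mean albumin above 4.0 the uncorrected limit mostly stops dosing early. For albumin means of 4.2-4.4, missed Day 7 cases are at most 0.75% (0.15 of 20).
- **Power.** The loss of 1.5 points matters little, because Protocol section 14 and the SAP plan no hypothesis testing, although the Synopsis lists a paired t test.

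**Conclusion.** The concern holds. The only calcium dosing stop is stated on a different quantity from the entry criterion and the planned safety measure, and the schedule lacks the albumin needed to reconcile them on Days 7 and 14. This is a contradiction in the text and depends on no assumed figure.

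The size does depend on assumptions: the correction formula, the albumin and calcium distributions, and no gel effect. On the Day 7 result, fewer than one subject in 20 is expected to be affected in either direction. The simulated cases are chance crossings of the limit, so they do not estimate how often gel-induced hypercalcaemia would be missed. The consequence for the primary analysis is slight. The correction should be made because a safety stop at 300,000 IU per dose should be unambiguous and should match the protocol's own definition of hypercalcaemia.

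**What to change.** 1. In section 13.1.1, state the stop as albumin-corrected serum calcium above 10.2 mg/dl, and give the correction formula, which no section currently provides.
2. Add serum albumin to the Day 7, 14 and 21 draws in the Synopsis visit list, Table 1, and sections 11.1.2 and 11.1.3. Day 21 comes after the last dose, so albumin there serves the promised safety summary and not the stop.
3. While editing that paragraph of 13.1.1, correct its 100,000-unit doses, which conflict with the 300,000 IU in sections 6 and 7.1. This is a separate error, but the same edit can deal with it.

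The cost is a phrase and a formula, one item added to the visit lists, and 3 × 20 = 60 albumin assays on blood already drawn, which the Synopsis commitment already implies. No visit or needle stick is added.

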13.2 Reporting of Safety Information

13.2.1 Definition of an Adverse Event (AE)

Any untoward medical occurrence in a clinical investigation subject, temporarily associated with the use of a medicinal product, whether or not considered related to the medicinal product.

Examples of an AE include:

- Exacerbation of a chronic or intermittent pre-existing condition including either an increase in frequency and/or intensity of the condition
- A new condition detected or diagnosed after investigational product administration even though it may have been present prior to the start of the study
- Signs, symptoms, or the clinical sequelae of a suspected interaction
- Signs, symptoms, or the clinical sequelae of a suspected overdose of either investigational product or a concurrent medication (overdose per se should not be reported as an AE/SAE)

Examples of an AE do not include:

- Medical or surgical procedure (e.g., endoscopy, appendectomy); the condition that leads to the procedure is an AE
- Situations where an untoward medical occurrence did not occur (social and/or convenience admission to hospital, such as for PK sampling convenience)

In this study, AEs may include pre- or post-treatment events that occur as a result of protocol-mandated procedures (i.e., invasive procedures, modification of a subject's previous therapeutic regimen).

13.2.2 Definition of a Serious Adverse Event (SAE)

An SAE is any untoward medical occurrence that, at any dose:

- a. results in death
- b. is life-threatening

Note: The term 'life-threatening' in the definition of 'serious' refers to an event in which the subject was at risk of death at the time of the event. It does not refer to an event, which hypothetically might have caused death if it were more severe.

- c. requires hospitalization or prolongation of an existing hospitalization

Note: In general, hospitalization signifies that the subject has been detained (usually involving at least an overnight stay) at the hospital or emergency ward for observation and/or treatment that would not have been appropriate in the physician's office or out-subject setting. Complications that occur during hospitalization are AEs. If a complication prolongs hospitalization or fulfills any other serious criteria, the event is serious. When in doubt as to whether 'hospitalization' occurred or was necessary, the AE should be considered serious.

Hospitalization for elective treatment of a pre-existing condition that did not worsen from baseline is not considered an AE.

- d. results in disability/incapacity

Note: The term disability means a substantial disruption of a person's ability to conduct normal life functions. This definition is not intended to include experiences of relatively minor medical significance such as uncomplicated headache, nausea, vomiting, diarrhea, influenza, and accidental trauma (e.g., sprained ankle) which may interfere or prevent everyday life functions, but do not constitute a substantial disruption.

- e. is a congenital abnormality / birth defect

- f. any event deemed by the Investigator as being a significant medical event.

Medical and scientific judgment should be exercised in deciding whether reporting is appropriate in other situations, such as important medical events that may not be immediately life-threatening or result in death or hospitalization, but may jeopardize the subject or may require medical or surgical intervention to prevent one of the other outcomes listed in the above definition. These should also be considered serious. Examples of such events are invasive or malignant cancers, intensive treatment in an emergency room or at home for allergic bronchospasm, blood dyscrasias or convulsions that do not result in hospitalization, or development of drug dependency or abuse.

13.2.3 Recording of AEs and SAEs

When an AE/SAE occurs, it is the responsibility of the Investigator to review all documentation (e.g., hospital progress notes, laboratory, and diagnostic reports) relative to the event. The Investigator will then record all relevant information regarding an AE/SAE into the CRF.

For each AE, start and stop dates, action taken, outcome, intensity (see Section 13.2.3.1) and relationship to study product (causality) (see Section 13.2.3.2) must be documented. If an AE changes in frequency or intensity during a study, a new entry of the event must be made in the CRF.

The Investigator will attempt to establish a diagnosis of the event based on signs, symptoms, and/or other clinical information. In the absence of a diagnosis, the individual signs/symptoms should be documented.

All details of any treatments initiated because of the AE should be recorded in the subject's notes and the CRF.

All AEs and SAEs will be followed until resolution, until the condition stabilizes, until the event is otherwise explained, or until the subject is lost to follow-up. Once resolved, the appropriate AE/SAE CRF page(s) will be updated. The Investigator will ensure that follow-up includes any supplemental investigations as may be indicated to elucidate the nature and/or causality of the AE or SAE. This may include additional laboratory tests or investigations, histopathological examinations, or consultation with other health care professionals.

13.2.3.1 Assessment of Intensity

The Investigator will make an assessment of intensity for each AE and SAE reported during the study. The assessment will be based on the Investigator's clinical judgment. Adverse events from the first dose of topical vitamin D gel will be assessed based on this general guideline:

- Mild; asymptomatic or mild symptoms; clinical or diagnostic observations only; intervention not indicated
- Moderate; minimal, local or non-invasive intervention indicated; limiting age-appropriate instrumental activities of daily
- Severe or medically significant but not immediately life-threatening; hospitalization or prolongation of hospitalization indicated; disabling; limiting self care activities of daily living
- Life-threatening consequences; urgent intervention indicated
- Death related to AE

Severity should not be confused with an SAE. Severity is a category utilized for rating the intensity of an event; and both AEs and SAEs can be assessed as severe. An event is defined as "serious" when it meets one of the pre-defined outcomes as described in Section 13.2.2 "Definition of an SAE."

13.2.3.2 Assessment of Causality

The Investigator is obligated to assess the relationship between investigational product and the occurrence of each AE/SAE. The Investigator will use clinical judgment to determine the relationship. Alternative causes, such as natural history of the underlying diseases, concomitant therapy, other risk factors, and the temporal relationship of the event to the investigational product will be considered and investigated.

The causal relationship to the study product assessed by the Investigator (or medically qualified delegate) should be assessed using the following classifications:

Not Related In the Investigator's opinion, there is not a causal relationship between the study product and the AE.

Unlikely	The temporal association between the AE and study product is such that the study product is not likely to have any reasonable association with the AE.
Possible	The AE could have been caused by the study subject's clinical state or the study product.
Probable	The AE follows a reasonable temporal sequence from the time of study product administration, abates upon discontinuation of the study product and cannot be reasonably explained by the known characteristics of the study subject's clinical state.
Definitely	The AE follows a reasonable temporal sequence from the time of study product administration or reappears when study product is reintroduced.

The causality assessment is one of the criteria used when determining regulatory reporting requirements.

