8.4 Replacement of Subjects

Subjects who withdraw or are removed from the study prior having their Day 7 blood draw for a reason other than a drug-related adverse event will be replaced.

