### **1.1 Analysis Populations**

*Safety Population:* all subjects who receive at least 1 dose of study drug and who have at least one post-dosing safety evaluation. All safety endpoints, baseline characteristics, and demographic data will be summarized using the Safety Population.

*Efficacy Evaluable Population:* all subjects who receive all 3 doses of study drug and have a follow up blood draw for vitamin D levels, or discontinue prior to completing dosing due to a drug-related adverse event. Vitamin D level data will be analyzed using the Efficacy Evaluable Population.

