#### **1.3.4 Safety Analyses**

Safety parameters will be listed and summarized using standard descriptive statistics.

Adverse event terms will be coded using the Medical Dictionary for Regulatory Activities (MedDRA) and will be summarized by dose. Incidence of AEs occurring during the study will be summarized by system organ class (SOC) and preferred term. Adverse events will also be summarized by causality and grade. Serious adverse events and AEs leading to discontinuation of study treatment will be listed separately.

Additional analyses will be performed if warranted upon review of the data.

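### The causality scale is not ordered: as worded, *Definitely* is easier to meet than *Probable*

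*Protocol*

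**What the plan says.** Protocol 13.2.3.2 has five categories: *Not Related*, *Unlikely*, *Possible*, *Probable* and *Definitely*. The last two are the ones at issue.

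- *Probable* needs reasonable timing after dosing, and the AE also "abates upon discontinuation of the study product and cannot be reasonably explained by the known characteristics of the study subject's clinical state". All three conditions must hold together.
- *Definitely* applies when "The AE follows a reasonable temporal sequence from the time of study product administration or reappears when study product is reintroduced". Either condition is enough.

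The same section says "The Investigator will use clinical judgment to determine the relationship" and asks for other causes to be looked into. It also directs that causality be assessed with these classifications and names causality as one criterion for regulatory reporting.

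The grading feeds one planned summary. SAP 1.3.4, like Protocol 14.3.4, states: "Adverse events will also be summarized by causality and grade".

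**The concern.** A causality scale is read as a gradient, with each step up demanding stronger evidence than the one below. Here the top step demands less than the step beneath it: it drops both abatement and the absence of another explanation.

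Take a headache on the day after gel application in a subject with known migraine. It can be *Possible*, because either the clinical state or the product could have caused it. It cannot be *Probable*, because the clinical state explains it. On timing alone it also meets *Definitely*. The protocol has no rule for an AE that fits more than one category.

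Safety is the secondary objective of this open-label trial of a novel gel. If two assessors can put the same event at *Possible* and at *Definitely*, each with support from the text, the by-causality summary does not show what its row labels say. The same grade also goes into the reporting decision.

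**Working it through.** The plan gives no figure for this point, so the check is a comparison of definitions.

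**Inputs.** From Protocol 13.2.3.2, four criteria, each met or not met: T = reasonable timing after dosing; A = abates on stopping; N = not reasonably explained by the clinical state; R = reappears on reintroduction. This gives 2 × 2 × 2 × 2 = 16 patterns. From Protocol 7.2: doses on Days 0, 7 and 14, follow-up to Day 21.

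**Step 1. Count the patterns.** The last column covers the 8 patterns in which the clinical state does explain the AE (N not met).

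| Definition | Rule | Patterns of 16 | Of the 8 with N not met |
|---|---|---|---|
| *Probable* | T and A and N | 2 | 0 |
| *Definitely*, as written | T or R | 16 − 4 = 12 | 3 × 2 = 6 |
| *Definitely*, 'and' for 'or' | T and R | 4 | 1 × 2 = 2 |
| *Definitely*, cumulative | T and A and N and R | 1 | 0 |

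Both *Probable* patterns also meet *Definitely* as written, and 12 − 2 = 10 patterns meet *Definitely* without meeting *Probable*. The nesting runs the wrong way. The counts describe logic; they are not frequencies of AEs.

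**Step 2. Test the obvious repair.** With 'and' in place of 'or', 4 patterns remain and only 1 of them meets *Probable*. The other 3 lack abatement, lack the exclusion of another explanation, or lack both. Only the cumulative rule places *Definitely* inside *Probable*.

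**Step 3. Test an exemption for AEs without reintroduction.** If R were required only where the product is given again, the rule for all other AEs would be T and A and N, which is *Probable*. Those AEs include any that start after the last application on Day 14 and any in subjects who stop treatment. The two grades would coincide there, so reappearance has to be required without exception.

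**Step 4. How much does timing screen out?** On schedule, the longest gaps since the latest dose are 7 − 0, 14 − 7 and 21 − 14, each 7 days. T is therefore often arguable. The documents do not say that 7 days is reasonable timing, so this shows a weak screen and not an automatic pass.

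**Step 5. Does the error reach the analysis set?** Under Protocol 14.1 and SAP 1.1, early stoppers stay evaluable if they "or discontinue prior to completing dosing due to a drug-related adverse event". Under Protocol 8.4, those who leave before the Day 7 draw "for a reason other than a drug-related adverse event will be replaced". None of these sections refers to the scale or says which categories count as drug-related. Two cut-offs can be assumed:

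- *Possible* or higher: the migraine example already counts as drug-related, so correcting *Definitely* changes nothing.
- *Probable* or higher: an AE that should be *Possible* could cross the line by being graded *Definitely*, but only in a subject who stops early because of that AE.

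The documents support neither cut-off and give no expected number of such subjects.

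**The case against.** The strongest defence is that no investigator grades by reading 'or' literally. The section requires clinical judgment and says that "Alternative causes, such as natural history of the underlying diseases, concomitant therapy, other risk factors" and timing are to be considered and investigated. This will restrain grading in practice, so it would be too strong to say that almost any on-study AE will be graded *Definitely*. It does not repair the text: the same section directs assessors to these classifications, and neither safeguard is a condition of *Definitely*.

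A reader might also infer that the misordered scale decides who is evaluable and who is replaced, with each misgraded early stopper shifting 1/20 = 5% of the evaluable set. The documents do not support this. Those rules turn on an undefined term, which is a separate gap that would remain with a perfectly ordered scale. The 5% is a headcount: missing values are not imputed, so a retained subject with no post-dose draw adds nothing to the mean change. Even a subject wholly lost costs little. With the plan's SDs of 4 and 12, the SD of the difference is √(16 + 144) = 12.65 (zero pre-post correlation assumed). For a difference of 10, two-sided alpha 0.05 and 90% power, an exact paired t calculation gives 19 subjects against the plan's 20. Power with 20, 19, 18 and 17 subjects is 0.918, 0.903, 0.885 and 0.864, a loss of about 1.5 to 2.1 points per subject. Protocol 14 and SAP 1 rule out formal testing in any case, although the synopsis mentions a paired t test.

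A reader might further infer that the safety results as a whole become uninterpretable. They do not. The skin endpoint counts any rash or reaction whatever its cause and has its own score in Protocol 13.1.1. AE incidence by system organ class and preferred term, the listings of serious AEs and of AEs leading to discontinuation, and the calcium and parathyroid hormone results do not use the causality grade.

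**Conclusion.** The point holds as a drafting error of minor severity. As written, the top category is logically weaker than the one below it, and an AE explained by the clinical state can meet it. The consequence is confined to the summary of AEs by causality and to the causality input to regulatory reporting. How far it affects reporting cannot be sized, because the documents do not say which categories trigger a report. Little or no effect on the evaluable population or on replacement has been demonstrated.

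The conclusion rests on reading 'or' in its ordinary sense and on taking the five categories as rising in strength, which is the order in which they are listed.

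**What to change.** In Protocol 13.2.3.2, before any AE is graded, redefine *Definitely* as all three *Probable* conditions and, in addition, reappearance when the study product is reintroduced. Allow no exception for AEs without reintroduction, and state that such AEs can be graded no higher than *Probable*. This changes grading only and is not a reason to re-expose anyone. SAP 1.3.4 can stand, since it refers only to causality in general.

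The cost is one reworded definition in the protocol. The downside is that fewer AEs can reach *Definitely*; those that begin after the Day 14 application cannot reach it within the planned dosing. If AEs from the three subjects reported in Protocol 5.2.2 have already been graded and will enter the same summary, regrade them under the new definition.
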